7.15 Immunogenicity

Immunogenicity will be presented as a descriptive table of Anti-rhAnnexin V-128 IgG and IgM antibodies assessment (by ELISA) at screening and at 30 and 56 days post-administration plus an addition sample taken at day 90 in case of previous positive result.

7.16 Disease Assessment

BASDAI, BASFI and BASMI scores for AS patients will be presented as a descriptive table at each visit.

DAS28 and ACR/EULAR scores for RA patients will be presented as a descriptive table at each visit.

7.17 ^{99m}Tc -rhAnnexin V-128 Scintigraphy

Descriptive statistics of the imaging findings with report of location and intensity of lesions at each imaging time point will be reported to determine the most suitable imaging time point post injection.

An association between annexin scintigraphy results and disease assessments (see Section 7.16) will be presented to assess diagnostic concordance.

These analyses will be taken care of by AAA's study physician and results will appended to the clinical study report.

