**Clinical assessment**

For RA diagnosed patients a clinical evaluation will be made at the screening visit, at Day 42 and Day 90. The DAS-28 (3items: tender joints, swollen joints and ESR) will be calculated. For AS beside the clinical evaluation including the search for enthesopathy – using the Maastricht Score -, assessments with BASDAI, BASFI and BASMI will be made.

The clinical assessment will be completed by the measurement of biological markers of inflammation (ESR, CRP and CBC).

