**Ultrasound assessment**

For RA patients only, an ultrasound examination of the 28 joints included in the DAS 28 will be made at screening, Day 42 and Day 90. Synovitis, power-doppler activity and erosions will be checked.

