5 STUDY SCHEMA

Study Procedures	Screening (±4 weeks)	Day 1	24 hours ¹	Day 30 ±3 days	Day 42 ±2weeks	Day 56 ±2weeks	Day 90 ±2weeks
Written informed consent	x						
Inclusion/exclusion criteria	x						
Medical history	x						
Concomitant medications including RA and AS treatment	x	x	x	x	x	x	x
Disease assessment (BASDAI, BASFI, BASMI for AS for AS patients, DAS28 scales including Ultrasound assessments for RA patients)	x				x		x
Physical examination	x				x		x
Vital signs (BP and HR)	x	x	x	x	x	x	x
Lab analysis (haematology, biochemistry; urine)	x		x	x	x		x
Venous/urine sampling (PK and dosimetry) ²		x ¹	x				
Immunogenicity by ELISA ³	x			x		x	x
Urine SEC-HPLC analysis ^{1,4}		x	x				
Pregnancy test	x	x			x		
Standard 12-lead ECG	x	x	x	x	x		x
rh-Annexin V-128 administration ⁵		x			x		
Bone scintigraphy ⁷	x						
Whole Body scintigraphic imaging ⁵		x	x		x		
Adverse Events	x	x	x	x	x	x	x

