14.3.5	Disease Assessment (BASDAI, BASFI, BASMI, DAS28, ACR/EULAR scores) at each visit and change from baseline	Safety
14.3.6	Listing of Anti-Annexin V-128 IgG and IgM antibodies Reactive results	Safety
14.3.7	Physical examination at each visit	Safety
14.3.8.1	Vital signs at each visit and change from baseline	Safety
14.3.8.2	Vital signs – Shifts from baseline	Safety
14.3.9.1	Overall Electrocardiogram interpretation	Safety
14.3.9.2	Electrocardiogram parameters at each visit and change from baseline	Safety

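### SAP 7.17 compares the scans only with whole-patient scores and does not name the scheduled 28-joint ultrasound as a comparator in RA

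*SAP*

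**What the plan says.** **Concordance analysis.** SAP 7.17 reports the location and intensity of lesions on the scan, then adds: "An association between annexin scintigraphy results and disease assessments (see Section 7.16) will be presented to assess diagnostic concordance".

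**What Section 7.16 contains.** For AS: "BASDAI, BASFI and BASMI scores for AS patients will be presented as a descriptive table at each visit". For RA: "DAS28 and ACR/EULAR scores for RA patients will be presented as a descriptive table at each visit". SAP 6.4 gives the same list, and Table 14.3.5 is titled "Disease Assessment (BASDAI, BASFI, BASMI, DAS28, ACR/EULAR scores) at each visit and change from baseline".

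**What is collected.** The protocol's ultrasound paragraph in Section 6 says that, for RA patients, "an ultrasound examination of the 28 joints included in the DAS 28 will be made at screening, Day 42 and Day 90". It adds: "Synovitis, power-doppler activity and erosions will be checked".

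**Where ultrasound appears in the SAP.** Only in the Section 5 schema, in the disease assessment row: "DAS28 scales including Ultrasound assessments for RA patients". Protocol Table 1 has the same row. No SAP endpoint, analysis, table, figure or listing title mentions ultrasound.

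**The concern.** One secondary objective (Protocol Section 2, SAP 3) is whether early imaging can evaluate lesions at baseline and again after a short period on the new treatment. The scan data are local: SAP 6.5 uses the number and place of lesions and counts per region of interest. The named comparators are not local. A patient may have a high DAS28 and several uptake foci, none of them in a joint with synovitis, and a patient-level association would still look favourable.

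Ultrasound of the DAS28 joints is the one scheduled follow-up measure aimed at the same anatomical sites. The protocol's background section describes it as a means of finding synovitis and erosions that other methods miss. If the plan is followed as written, the concordance result cannot answer the question about lesions, although data that could help are scheduled.

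A smaller point concerns ACR/EULAR. Protocol Section 4 uses that score to diagnose RA and DAS28 to evaluate patients afterwards. Table 1 schedules no repeat, yet SAP 6.4 and 7.16 tabulate it at every visit.

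**Working it through.** The plan gives no precision figure for concordance. Its only sizing figure reproduces: 20/(1 − 0.10) = 22.2, rounded up to 23 recruits. It has no bearing on this point.

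**Step 1: does DAS28 bring ultrasound in?** The schema wording could suggest so. The protocol's clinical assessment paragraph says otherwise: "The DAS-28 (3items: tender joints, swollen joints and ESR) will be calculated". Ultrasound is therefore a separate measurement made on the same joints.

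**Step 2: what could be paired.** Inputs are 10 RA patients (Protocol Section 2), 28 joints, three ultrasound visits (screening, Day 42, Day 90) and two scan visits (Day 1, Day 42).

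- Ultrasound joint examinations: 10 × 28 × 3 = 840.
- Pairable with a scan: 10 × 28 × 2 = 560, or 280 per scan. Day 90 has no scan.
- SAP 4.2 says that recruitment stopped early with at least 80% of the planned sample evaluable. If the shortfall falls evenly on RA and AS (assumption), 8 RA patients give 224 joints per scan.
- SAP 6.5 keeps only patients with anterior and posterior planar images at 1 h and 2 h on both Day 1 and Day 42. The protocol fixes both times on Day 1 for only two groups of three patients and leaves the Day 42 time open. If that restriction also governs 7.17, and 6 patients qualify, 3 of them with RA (assumption, not a bound), 84 joints remain per scan.

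**Step 3: the patient-level analysis as planned.** For an observed correlation of 0.5 between a scan summary and a score, the Fisher z interval is tanh(atanh 0.5 ± 1.96/√(n − 3)). This gives −0.19 to 0.86 with 10 patients and −0.32 to 0.89 with 8.

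**Step 4: illustrative joint-level precision.** The design effect is 1 + 27 × ICC: 3.7, 9.1 and 14.5 for assumed ICCs of 0.1, 0.3 and 0.5. For 280 joints the effective numbers are 75.7, 30.8 and 19.3. For an assumed agreement of 70%, SE = √(0.21 × design effect / joints), against √(0.21/n) for one yes/no result per patient.

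| RA patients | Joints per scan | SE, one result per patient | SE, ICC 0.1 | SE, ICC 0.3 | SE, ICC 0.5 |
|---|---|---|---|---|---|
| 10 | 280 | 0.145 | 0.053 | 0.083 | 0.104 |
| 8 | 224 | 0.162 | 0.059 | 0.092 | 0.117 |
| 3 | 84 | 0.265 | 0.096 | 0.151 | 0.190 |

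The ratio of joint-level to patient-level SE is √(design effect/28), or 0.36, 0.57 and 0.72, whatever the number of patients. These are different quantities, and DAS28 is a numeric score, so the table shows how much information is available. It does not measure a like-for-like gain.

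**The case against.** **The SAP may already include ultrasound.** Both schedules put it in the disease assessment row, 7.17 refers to disease assessments, and Listing 16.2.4.10 carries that title. A reader might infer from its absence in 7.16 that the sponsor decided to exclude ultrasound, or that it will not be reported at all. The documents support neither inference. What stands is that 7.17 points to Section 7.16, which does not name ultrasound, and a listing is not a concordance analysis.

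**Patient-level scores suit part of the aim.** The study also seeks to predict response to treatment, for which an activity score is a sensible comparator. All testing is exploratory (SAP 7.1.1), SAP 4.2 foresees a review of which secondary analyses are worth doing, and the sponsor's study physician handles 7.17. The documents never call ultrasound a reference standard. This argues for adding the joint-level comparison beside the scores, labelled exploratory, and not for replacing them.

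**The data may be too sparse or too coarse.** Joint-by-joint recording is an inference, since the CRF is not available. The protocol plans repeat acquisitions on symptomatic joints and target-to-background ratios (TBR) for inflammatory joints, so uptake in quiet joints may need new reading. Screening has a 4-week window, so the ultrasound paired with Day 1 may be weeks old. Standard GEE or bootstrap intervals are unreliable with 10 or fewer patients. All of this stands and shapes the fix. Sparse data do not remove the point: with 3 RA patients the joint-level SE is 0.096 to 0.151 at ICC 0.1 to 0.3, against 0.265 for 3 patient-level results.

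**Conclusion.** The concern holds as a gap in specification. The concordance analysis names only patient-level comparators, which cannot show whether uptake matches an inflamed joint, and a scheduled joint-level measure is left without an analysis. The argument rests on the text and on the objective, not on precision.

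The size is bounded: RA patients only, at most 280 joints per scan, and fewer under early stopping and SAP 6.5. A reader might take the table to mean that the joint-level analysis cuts the standard error by a known factor. The documents do not support that: they give neither the ICC nor the agreement, and the two analyses estimate different things.

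The objective is secondary and the analysis exploratory, so this should be corrected but does not touch the primary safety objective. The ACR/EULAR wording is a separate and minor inconsistency.

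**What to change.** In SAP 7.16 and 7.17:

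- Name ultrasound synovitis and power Doppler as the joint-level comparator for RA, alongside the patient-level scores.
- Pair the Day 1 scan with the screening ultrasound and report the interval between them. Pair the Day 42 scan with the Day 42 ultrasound.
- Cross-tabulate uptake (yes/no) against ultrasound for each joint assessable on the images. Count the joints that are not assessable. Give TBR where regions of interest are drawn.
- Report agreement, sensitivity and specificity descriptively and as exploratory. Add per-patient summaries and an interval that allows for clustering by a small-sample method, for example a t interval over the patients' own agreement proportions.
- State whether the image restriction in 6.5 applies to this analysis.
- Remove ACR/EULAR from the follow-up visits in 6.4, 7.16 and Table 14.3.5. If some other ACR/EULAR score was meant, define it.

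If ultrasound is not to be used, say so and give the reason.

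The cost is a SAP revision, some programming and some extra image reading, with no new patient visits. Some small joints will not be resolved on planar images. The sponsor must first confirm that the CRF holds ultrasound findings per joint. If the database is already locked, label the analysis post hoc.

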### **3 STUDY DESIGN**

#### **Study Outline**

This is a monocentric, open label, Phase I-IIa study.

Patients who have signed the informed consent and are eligible for study participation according to the inclusion and exclusion criteria will receive a single intravenous bolus of 99mTc-rhAnnexin V-128 on Day 1 and a single intravenous bolus of 99mTc-rhAnnexin V-128 6 weeks later (+/- 2 weeks).

All patients will start a new RA or AS treatment on Day 2.

In order to minimize the risks for the study population, patients will be enrolled with a minimum of 2-week interval.

Details on study assessments are provided in Protocol Section 6 and Table1.

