99mTc-rhAnnexin V-128 administrations:patients will be injected intravenously with 250 MBq of 99mTc-rhAnnexin V-128 and then the whole body planar imagings (GE Infinia Hawkeye IV camera, (8 cm/min, 1024x256 matrix; zoom 1) will be performed and repeated acquisitions on symptomatic joints. Standard quality control of the camera will be performed every day before patient imaging. Peak will be centered on 140KeV with a 20% windowing; a LEHR collimator will be used. A dual-SPECT would be acquired centered on the thorax and abdomen at 1h after injection centered (2\*60 projections of 10 seconds each, 128x128 matrix, zoom 1). The use of the whole-body and SPECT data for dosimetry will be discussed further in the Dosimetry section

Semi-quantitative assessment of inflammatory joints will be performed in terms of TBR as well as by calculating the relative uptake between pre and post treatment in ROI/VOIs. ROI and VOI defined and use in the different scintigraphies will strictly have the same pixel size and localization; they will be measured in counts.

In case a suspected anomaly is found at imaging, it would be reported to the rheumatologist and the patient's general practitioner.

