6.5 Imaging assessments

To assess the suitability of 99mTc-rhAnnexin V-128 imaging for detecting RA or AS lesions before and after short term treatment by observing qualitatively the number and location of lesions at each imaging point and calculating the intensity of lesion uptake (specific) as well as quantitatively through assessment of radiotracer uptake by geometric mean of counts/ROI on anterior and posterior planar images. Only patients with available anterior and posterior planar imaging data at 1h and at 2h post-injection at both Day 1 and Day 42 assessments will be considered for this analysis.

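### The plan does not name the reader of the annexin scans or mask that reader to visit or clinical scores, leaving the qualitative lesion findings and their concordance with disease scores open to expectation bias

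*SAP*

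**What the plan says.** **Design.** The protocol (section 3, Study Outline) states: "This is a monocentric, open label, Phase I-IIa study". The same section has every patient start a new RA or AS treatment on Day 2. The first annexin scan is on Day 1 and the second at Day 42 ± 2 weeks.

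**Imaging outcome.** SAP 6.5 assesses lesions before and after short-term treatment in two ways. One is qualitative: "observing qualitatively the number and location of lesions at each imaging point and calculating the intensity of lesion uptake". The other is quantitative: "assessment of radiotracer uptake by geometric mean of counts/ROI on anterior and posterior planar images". The protocol (section 6, Imaging) adds target-to-background ratio and a pre/post comparison made "by calculating the relative uptake between pre and post treatment in ROI/VOIs".

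**Rule on regions.** The same protocol section says: "ROI and VOI defined and use in the different scintigraphies will strictly have the same pixel size and localization".

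**Who does the analysis.** SAP 7.17 plans descriptive statistics of lesion location and intensity and an association between scintigraphy and the disease assessments, to judge diagnostic concordance. It then says: "These analyses will be taken care of by AAA's study physician and results will appended to the clinical study report".

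**What is absent.** Neither document provides for a masked read, a random reading order, a second or independent reader, or a lock on readings before they are set against the clinical scores. Neither names the person who calls lesions or draws regions.

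**The concern.** Deciding whether a focus of uptake is a lesion, and how intense it is, takes judgement. Because all patients start therapy between the two scans, the visit label reveals treatment status. DAS28 or the BASDAI/BASFI/BASMI set is also collected at the Day 42 visit, so the clinical result may be available alongside the scan. Nothing in the plan keeps either from the reader.

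Two results are at stake: the before/after change in lesions and the agreement between scintigraphy and disease scores. They carry the third secondary objective, and they bear on the aims in protocol section 2 of predicting and assessing response to treatment. A reader who expects improvement may call fewer lesions on the later scan. A reader who knows the score may resolve doubtful foci to match it. There is no control arm against which such a shift would show.

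**Working it through.** No figure in the plan measures reader agreement or reader bias, so this check sets the provisions side by side.

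1. **Is the visit known?** Day 1 always precedes the new therapy, and Day 42 follows it by plan (protocol section 3). Without masking, visit equals treatment status.

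2. **Is the clinical score known?** Disease assessments are scheduled at screening, Day 42 and Day 90 (protocol Table 1). SAP 7.17 gives the lesion findings and their association with those scores to the same sponsor physician, and sets no order in which the two must be fixed.

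3. **Does any existing provision mask the reader?**
 - The common-region rule (protocol section 6, Imaging) fixes size and position across scans. It limits freedom in the count-based comparison, but does not govern qualitative lesion calls or say what the person placing the regions may know.
 - The request that baseline determinations be repeated by the same individual (protocol section 11, Data Review) helps consistency. It does not mask, and it allows recall of the baseline scan.
 - Patient ID coding (protocol section 4) hides identity, not visit or score.

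4. **Would another check catch it?** The SAP's lists of tables and figures (10.1, 10.2) contain no annexin scintigraphy summary. Section 10.3 has only subject listings for bone scintigraphy and whole-body planar imaging. The imaging results are appended to the study report, so no imaging summary is specified for the output checks in SAP 8.1.

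5. **Which results are exposed?** Qualitative number, location and intensity: fully. Concordance with disease scores: fully, in so far as it uses those readings. Pre/post counts per region: less, because of the common-region rule.

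6. **Volume to mask.** With one annexin scan visit before and one after the start of therapy per patient:
 - planned sample: 20 × 2 = 40 patient-visits;
 - after the early stop to recruitment, at the 80% given in SAP 4.2: 0.80 × 20 = 16 patients, and 16 × 2 = 32 patient-visits;
 - possibly fewer, because SAP 6.5 admits only patients with 1 h and 2 h anterior and posterior planar data at both visits.

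7. **Effect on other figures.** None. The recruitment figure reproduces (20 / 0.90 = 22.2, rounded up to 23) and does not depend on how scans are read.

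**The case against.** The strongest reply is that SAP 7.17 assigns analyses, not the primary read. Assessments take place in the site's Nuclear Medicine and Rheumatology departments (protocol section 6), scans and their reports are site source documents (section 11), and suspected anomalies go back to the rheumatologist and general practitioner. A site read is quite possible. This stands: a reader might infer that the sponsor's physician reads the scans knowing each patient's response, but the text does not say so. It shows that the reader is unspecified and that nothing prevents such knowledge, whoever reads.

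Second, the quantitative comparison is already protected by the common-region rule. This largely stands, and the point rests on the qualitative reading and the concordance.

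Third, 7.17 gives its lesion description the purpose of choosing the best imaging time after injection, where expectations about treatment matter little. That is true of that sentence. The before/after purpose is in SAP 6.5, and the association with disease scores is in 7.17 itself.

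Fourth, imaging is a secondary objective, the summaries are descriptive, all testing is exploratory (SAP 7.1.1) and the sample size has no power basis. This limits the consequence. It does not remove the problem, since a descriptive summary can carry a systematic bias as readily as a test can.

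Fifth, masking would be imperfect. Acquisitions are repeated on symptomatic joints, so the images may carry clinical cues, and a reader who has already seen the cases may remember them. This stands: masking reduces the bias but cannot be said to remove it.

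**Conclusion.** The gap is real and worth correcting. As written, the plan leaves the qualitative lesion findings and their concordance with DAS28 and BASDAI/BASFI/BASMI open to expectation bias, and masked random-order reading by the same reader would reduce that at little cost.

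The size of the bias cannot be given. A reader might be tempted to derive one by applying an assumed misclassification rate to 28 joints per RA patient. The documents do not support that: the 28-joint set belongs to DAS28 and the ultrasound examination, no 28-joint scintigraphic score is defined, and nothing says what share of joints would be borderline. Nor do the documents show that bias has occurred; its likely direction is a matter of reasoning.

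The conclusion assumes that no separate reading manual imposes masking; neither document refers to one for the annexin scans. The primary safety objective, the sample size and the significance level are unaffected. This is a change that should be made, not one on which the trial's main conclusion depends.

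**What to change.** In SAP 6.5 and 7.17:

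- Name, by role, who reads the annexin scans and who draws the regions.
- Require de-identified scans to be read in random order, masked to visit, disease scores and ultrasound findings.
- Carry the protocol's common-region rule into the SAP, so that paired scans use regions of the same size and position.
- Lock the readings before they are merged with clinical data for the association.

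The bone scan is left out of the masking list because the common-region rule may extend to it.

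The SAP's initial version is dated 26/01/2018, after recruitment was to stop by the end of September 2017, so some scans may already have been read. If they were read unmasked, have the same reader repeat the reading masked, or state in the study report that the reading was unmasked.

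**Cost.** De-identifying and shuffling at most about 40 patient-visits, about 32 at 80% of the planned 20, and possibly fewer under the SAP 6.5 restriction. A re-read may be needed. No extra patients, scans or readers are required. Some cues from acquisitions on symptomatic joints will remain, and reproducibility of a single reader is not addressed.

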7.18 Other Data

Other data, including informed consents, study administration and analysis sets will be listed by subject.

STA01form01v3

7.19 Changes to the Planned Analysis

There were no changes to the planned statistical analysis.

8 DELIVERABLES

8.1 Statistical Outputs Validation

█████ CRO seeks to ensure the quality of the results provided for the study in the form of tables and listings, and the derived datasets used in their creation according to █████ CRO Standard Operating Procedures (SOP).

The entire set of tables, listings, and figures will be checked for accuracy, completeness, and consistency prior to inclusion in the final clinical study report.

